## 2 PROTOCOL SYNOPSIS

TITLE: A Pilot Synaptic Vesicle Glycoprotein 2A (SV2A) PET Study to Evaluate the Effect of CT1812 Treatment on Synaptic Density in Participants with Mild to Moderate Alzheimer's Disease
SPONSOR: Cognition Therapeutics Inc.
PROTOCOL NUMBER: COG0105
CLINICAL STUDY PHASE: Phase Ib/2a
STUDY DRUG PRODUCT: CT1812
STUDY OBJECTIVES: Primary: To evaluate the safety and tolerability of CT1812 in AD patients  Secondary: 

To evaluate the effect of CT1812 on brain synaptic density in Alzheimer's disease (AD) patients using the SV2A PET ligand C-UCB-J

To evaluate the effect of CT1812 on cognitive and clinical outcomes in AD patients using the ADAS-Cog11 and ADAS-Cog13 (derived from ADAS-Cog14), NTB, ADCS-ADL, MMSE, CDR-SB and ADCS-CGIC

To evaluate the effect of CT1812 on brain activity in AD patients using FDG PET and resting state functional MRI

To evaluate the effect of CT1812 on brain volume in AD patients using volumetric MRI

To evaluate the effect of CT1812 on CSF pharmacodynamics in AD patients through measurement of CSF A<math>\beta</math> 40, A<math>\beta</math> 42, A<math>\beta</math> oligomers, tau, phospho-tau, neurogranin, synaptosomal-associated protein-25 (SNAP25), synaptotagmin and NFL. Additional CSF biomarkers are listed in the statistical analysis plan.

To evaluate the plasma and CSF concentrations of CT1812 in AD patients

 Exploratory: █ [REDACTED] █ [REDACTED]
STUDY DESIGN This is a single-center, Phase 1b randomized, double-blind, placebo-controlled parallel-group trial in adults with mild to moderate AD.
STUDY PROCEDURES After consenting to participate in the study, screening procedures will occur between Days -60 and -1. Eligible participants will be randomized in a 1:1:1 (300 mg active: 100 mg active: placebo) ratio. The first dose of study drug will be administered in the clinic after all baseline procedures have been conducted. For the remainder of study days, participants will ingest study drug each morning at home. Participants and their study

partners will return to the clinic for repeat psychometric/neurologic testing, safety studies and PK and PD sample collection approximately 12 times during the course of the study. Participants who prematurely discontinue the study for any reason will be asked to attend the final/ early discontinuation visit but are not required to attend a follow up visit unless deemed necessary at the discretion of the investigator.

**Safety Stopping Rules:**

**For all participants:**

The occurrence of any one of the following events will result in suspension of administration of study drug in all participants until safety information can be further reviewed by the Sponsor and Medical Monitor.

- Two occurrences of the same or similar serious adverse event (SAE) assessed as probably or possibly related to dosing with investigational product
- Two or more different participants with the same or similar severe AE assessed as probably or possibly related to dosing with the investigational product
- Four or more participants with the same or similar moderate AE which is possibly or probably related to dosing with investigational product

Under these circumstances, the Sponsor and Medical Monitor will review the available safety data and, in consultation with the study principal investigator, recommend whether dosing should continue, or if study drug administration at one of the three study doses should be terminated, or if additional monitoring procedures or safety precautions need to be employed.

If a stopping rule is achieved, selective unblinding of the participants involved may be performed by the Sponsor to determine if the SAEs/AEs are isolated to a single dose group or if they occurred in placebo participants.

The study or a dose group may also be terminated if the Medical Monitor, Study Director and Sponsor, in consultation with the lead principal investigator, determine that any adverse event(s) are occurring that are intolerable or pose a medically unacceptable safety risk.

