**For individual participants:**

Participants who develop a severe adverse event or laboratory abnormality will not receive any additional doses and will be monitored until resolution of the AE or the return of laboratory abnormality to the acceptable screening value(s). Study drug may be re-initiated after consultation with medical monitor and sponsor. Any participant with:

- elevated ALT or AST greater than 5 X ULN should have dosing with study drug stopped and have laboratory tests repeated every 3-4 days until levels return to less than or equal to 1.5 X ULN. If the medical monitor and investigator are in agreement, study drug may be continued while a confirmatory ALT/AST is obtained within 3 days. If the confirmatory ALT/AST tests are below 5 X ULN, study drug may be continued. The frequency of the laboratory tests may be modified after discussion with the medical monitor if the liver enzymes are in a decreasing trend.
- elevated ALT or AST greater than 3 X ULN in combination with total bilirubin > 2 X ULN or INR > 1.5 X ULN OR an ALT or AST > 3 X ULN with the appearance of fatigue, nausea, vomiting, right upper quadrant pain or tenderness, fever, rash, and/or eosinophilia (>5%) should have dosing with study drug stopped and have

laboratory testing repeated every 3-4 days. If the medical monitor and investigator are in agreement, study drug may be continued while a confirmatory laboratory testing is obtained within 3 days. If these criteria are no longer met, study drug can be continued at the discretion of the medical monitor and investigator. The frequency of the laboratory tests may be modified after discussion with the medical monitor if the laboratory tests are trending towards normal.

- An increase in serum creatinine by 0.3 mg/dL (24.4 micromol/L) or 150% of baseline that is without clinical explanation of another etiology will result in repeated serum chemistry testing within 3-7 days. If the serum creatinine elevation is confirmed on repeated testing the study drug will be discontinued. If the serum creatinine elevation resolves upon subsequent testing after study drug is discontinued the study drug may be restarted with serum creatinine monitoring at the discretion of the medical monitor and investigator.

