### **4.3 Clinical Experience**

CT1812 has been administered safely with good tolerability in over 60 healthy volunteers in a placebo-controlled Phase 1a trial (COG0101). Six single and three multiple dose cohorts (QD, 14 days) were observed under close inpatient stay (N=6-8 treated, 2 placebo per cohort). Plasma concentrations of drug were shown to be approximately dose proportional across two orders of magnitude [0.13-14.93 mg (free base equivalent)/kg], and accumulation was minimal. Peak concentrations of CT1812 were reached within 1 to 2 hours and the plasma half-life was shown to be approximately 12 hours. Adverse events were mostly mild to moderate in severity and principally included headache, nausea, vomiting, diarrhea, constipation, abdominal pain, dyspepsia, upper respiratory tract infection, lightheadedness, syncope, myalgia, dizziness, rash and pain at the lumbar puncture site in those subjects who had lumbar punctures. There was only one AE of severe intensity, being an SAE of upper respiratory tract infection, occurring in one subject in the 840 mg dose of the multiple ascending dose (MAD) study, believed to be unrelated to study drug based on a similar pattern of URTIs in subjects receiving drugs other than CT1812 in the study unit during the same time period. One subject in the multiple dose cohort study developed a rash while on study drug. This subject showed improvement after discontinuing CT1812.

No evidence of renal toxicity has been observed to date based on routine measures of renal function (serum creatinine, blood urea nitrogen [BUN]) or cystatin C.

Four subjects in the MAD study showed an increase in liver function tests below 3X the upper limit of normal (including one subject on placebo). Subsequent studies will closely monitor liver enzyme parameters to determine if these were sporadic findings or possibly drug-related.

In COG0103 15 healthy volunteers evaluated potential effects of CT1812 on the disposition of sensitive substrates of selected CYP isoenzymes CYP2C19 (omeprazole), CYP2C9 (tolbutamide), CYP2D6 (dextromethorphan), and CYP3A4/5 (midazolam). Subjects were administered the probe drugs on Day -2 and pharmacokinetic (PK) evaluations performed. On Days 1 through 6, each subject took CT1812 560 mg. The CT1812 dose on Day 6 was taken

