concomitantly with the probe drug cocktail, and PK evaluation was conducted. No significant interaction was observed for isoenzymes 2C19 and 2C9. A weak drug interaction was observed between steady-state CT1812 and midazolam 4 mg (CYP3A4). Midazolam area under the concentration-time curve ( $AUC_{last}$ ) and the  $AUC_{last}$  ratio (parent to metabolite) decreased by 24% and 28%, respectively, when midazolam 4 mg was taken with steady state CT1812 than when midazolam was taken alone. A weak drug interaction was observed between steady-state CT1812 and dextromethorphan 50 mg (CYP2D6), as indicated by a 1.75-fold and 2-fold increase in dextromethorphan  $AUC_{last}$  and  $C_{max}$ , respectively, following the combination treatment relative to dextromethorphan alone; however, the dextromethorphan/dextrorphan  $AUC_{last}$  ratio was similar between treatments. Based on the small magnitude of the interactions observed in this study for the isoenzymes CYP2D6 and CYP3A4, clinically meaningful implications are unlikely.

A Phase 1a/2 trial (COG 0102) has completed enrollment in Australia, evaluating the safety and pharmacokinetics of three doses of once a day CT1812 (90 mg, 280 mg, 560 mg) dosed for 28 days in subjects with mild to moderate Alzheimer's disease. This study enrolled 19 subjects in a 1:1:1:1 ratio of these doses vs. placebo. In general, all doses were relatively well tolerated, with no SAEs. All AEs were considered mild or moderate. While there was an increased frequency observed in total AEs with increasing dose, the small number of treated subjects does not permit definitive conclusions regarding the incidence of AEs by dose in a larger study population. Specific AEs which were noted to occur with greater frequency at the 560 mg dose included transient lymphocytopenia, nausea, vomiting, headache, fatigue, and depression. These AEs resolved in most instances while treatment was ongoing; one subject at the 560 mg dose experienced an ALT increase of 4.7 X ULN which resolved to normal levels after discontinuation of study drug. Cognitive outcomes were similar across the treatment groups. Plasma CT1812 concentration increased approximately dose proportionally, with a dose dependent increase in CSF concentration. CSF concentrations at all tested doses were > 80% of estimated brain PGRMC-1 receptor occupancy, which was the threshold associated with efficacy in preclinical studies.

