#### 15.2.2.2 Assessment of Intensity

The intensity of each AE will be rated according to the following 3-point scale:

- **Mild:** Awareness of signs or symptoms, but no disruption of usual activity
- **Moderate:** Event sufficient to affect usual activity (disturbing)
- **Severe:** Inability to work or perform usual activities (unacceptable)

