- **Is an important medical event.** Important medical events are events that may not be immediately life-threatening or result in death or hospitalization but may jeopardize the participant or may require intervention to prevent one of the other outcomes listed in the definition above. Examples of important medical events include AEs that suggest a significant hazard, contraindication or precaution, occurrence of malignancy or development of drug dependency or drug abuse. Medical and scientific judgment should be exercised in deciding whether events qualify as medically important.

An AE caused by an overdose or medical error is considered serious if a criterion listed in the definitions above is fulfilled.

The following are not considered SAEs:

- A pre-existing condition that is present prior to or at the start of the study that did not worsen
- Hospitalizations for treatment which were elective or preplanned, for a pre-existing condition unrelated to the indication under study that did not worsen
- Admission to a hospital or other institution for general care, not associated with any deterioration in condition.

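### The four-case stopping rule counts only moderate AEs, so read literally three moderate plus one severe related case does not automatically suspend dosing

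*Protocol*

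**What the plan says.** The Protocol synopsis (Safety Stopping Rules, For all participants) and section 7.3.1 carry the same three triggers. Meeting any one suspends study drug in all participants until the sponsor and medical monitor have reviewed safety. All three concern the same or similar event, judged possibly or probably related:

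- Bullet 1: two occurrences of an SAE.
- Bullet 2: two or more participants with a severe AE.
- Bullet 3: "Four or more participants with the same or similar moderate AE which is possibly or probably related to dosing with investigational product".

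Section 15.2.2.2 gives each AE one of three grades (mild, moderate, severe). Section 15.2.2 warns that seriousness is not to be confused with intensity, so a severe AE need not be an SAE.

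Other text bears on the same situation. For individuals, "Participants who develop a severe adverse event or laboratory abnormality will not receive any additional doses". The study or a dose group may also be terminated if the responsible parties determine that "any adverse event(s) are occurring that are intolerable or pose a medically unacceptable safety risk". Under section 15.1.1 a safety committee receives AE data every two weeks and meets at least quarterly.

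**The concern.** A stopping rule should not become less likely to fire when a case gets worse. Here, four participants with a moderate related AE suspend dosing. If one of the four is severe instead, the moderate count falls to three and the severe count is only one, so neither bullet 3 nor bullet 2 is met.

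The documents name both grades when they mean both. Note 11 to the schedules of assessments requires follow-up of related AEs that are moderate or severe, and SAP Table 14.3.1.5 is titled for AEs of at least moderate intensity. Bullet 3 has no such qualifier in either place.

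At stake is an automatic pause for review in a trial whose primary objective is safety and tolerability. The sponsor's selective unblinding, which would show whether the cases cluster in one dose group, is also tied to a stopping rule having been met.

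**Working it through.** **The rule.** The plan states no operating characteristics for these rules, so there is no figure to reproduce. Let *m* and *s* be the numbers of participants whose worst grade of one same-or-similar related AE is moderate or severe.

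- As written, bullets 2 and 3 fire if *s* ≥ 2 or *m* ≥ 4.
- With moderate or greater in bullet 3, they fire if *s* ≥ 2 or *m* + *s* ≥ 4.

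The wordings can differ only when *s* ≤ 1 and *m* ≤ 3 (the written rule is silent) while *m* + *s* ≥ 4. That leaves *m* = 3, *s* = 1 and nothing else. Enumeration for 14, 21 and 25 participants confirms this.

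**The pattern against the rules.** Three moderate cases and one severe case, at most one of the four serious:

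| Rule | Needed | Present | Met |
|---|---|---|---|
| Bullet 1, related SAEs | 2 | 0 or 1 | no |
| Bullet 2, severe | 2 | 1 | no |
| Bullet 3, moderate | 4 | 3 | no |

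If two of the four cases are SAEs, bullet 1 fires under either wording.

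**Size.** Participant numbers come from the Protocol: 21 randomized and at most 25 dosed (section 9.1), 7 per arm and so 14 on active drug (section 17.2). Event rates are assumed. The difference between the wordings is the trinomial probability of exactly (3, 1):

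P = n! / (3! 1! (n−4)!) × p_m³ × p_s × (1 − p_m − p_s)^(n−4)

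For n = 21 the coefficient is 21 × 20 × 19 × 18 / 6 = 23,940.

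- p_m = 5%, p_s = 0.5%: 23,940 × 0.05³ × 0.005 × 0.945¹⁷ = 0.0057. The rule fires in 2.37% of trials as written and 2.95% as reworded.
- p_m = 10%, p_s = 0.5%: 23,940 × 0.10³ × 0.005 × 0.895¹⁷ = 0.0182. The rule fires in 15.63% as written and 17.45% as reworded.

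Bullet 1 is left out. It fires identically under both wordings, so including it could only shrink the difference.

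| p_m / p_s | n = 14 | n = 21 | n = 25 |
|---|---|---|---|
| 5% / 0.5% | 0.14 points | 0.57 | 0.96 |
| 10% / 0.5% | 0.66 | 1.82 | 2.46 |

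**Why a low severe rate.** Protocol section 4.3 reports for COG0101, with over 60 volunteers on drug: "There was only one AE of severe intensity, being an SAE of upper respiratory tract infection", believed unrelated. For COG0102, with 19 patients: "All AEs were considered mild or moderate". Taking 60 plus an assumed 14 of the 19 on active drug gives 0 related severe AEs in about 74 people. The one-sided 95% upper limit is 1 − 0.05^(1/74) = 4.0%. That limit is for any related severe AE, and one AE type can only be a part of it.

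**Stress cases (n = 21).** 8%/2% gives 4.1 points, 10%/3% gives 6.7 and 12%/4% gives 8.5.

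**Order of recording.** A severe case may first have been recorded as moderate. Assume half are. If worsening comes after the other three cases are recorded, bullet 3 has already fired, so the factor is 1 − 0.5 = 0.5. If worsening comes before the next case, bullet 3 fires only when that case is the fourth, so the factor is 1 − 0.5 × 0.25 = 0.875. The 0.57 to 1.82 range then becomes about 0.3 to 1.6 points.

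**The case against.** **Severe includes moderate.** An event that prevents usual activity also affects it, so a medical monitor could count the severe case toward the four. Many would. But each AE receives one grade, and the documents elsewhere write out both grades when they want both. The sensible reading is available, but the text does not secure it.

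**Little is lost.** Suspension is temporary. In the 3 + 1 pattern the participant with the severe AE is already off drug, and restarting requires the medical monitor and sponsor, who also run the study-level review. The safety committee sees AE data every two weeks. ALT/AST, creatinine and calcium have numeric individual stopping limits that do not depend on intensity grade, and these cover the most foreseeable toxicities. An AE that "may jeopardize the participant or may require intervention to prevent one of the other outcomes listed in the definition above" can be classed as an SAE, and two such cases fire bullet 1. All of this stands and is why the point is small. A reader might infer that participants in this pattern are unprotected, and the documents do not support that. What remains is that every one of these routes is individual, discretionary or dependent on a further classification.

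**The charter may settle it.** SAP section 5.3 refers to a safety committee charter that was not available for this review. It might say how cases are counted. The statement that nothing resolves the wording covers the Protocol and SAP only.

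**Conclusion.** The point holds as a narrow wording defect in a stated safety rule, worth correcting but not alarming. Exactly one combination of grades is affected, three moderate and one severe, provided that fewer than two of the cases are SAEs. One more moderate or severe case closes the gap, and so does worsening of one of the three moderate cases to severe, because bullet 2 then fires. If four moderate cases are recorded first, dosing is already suspended and later worsening does not undo that.

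Under assumed rates of 5% to 10% moderate and 0.5% severe for one AE type, the wordings differ in about 0.6% to 1.8% of trials at n = 21, and 0.1% to 0.7% if only the 14 active participants are at risk.

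Two stronger readings are tempting:

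- **The gap affects 4% to 9% of trials.** Those figures need a 2% to 4% severe rate for a single AE type, and the 4% limit applies to all related severe AEs together. They are stress cases. Earlier multiple dosing lasted at most 28 days, against 24 to 48 weeks here, so higher rates are not excluded, but nothing in the documents supports them as expected values.
- **The rules neglect severe events.** They do not: two severe cases suspend dosing on their own.

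**What to change.** In bullet 3, in both the synopsis and section 7.3.1, replace *moderate AE* with *AE of moderate or greater intensity*. Keep the threshold of four and leave bullets 1 and 2 as they are. The SAP needs no change.

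The cost is one bullet edited in two places. A temporary suspension becomes more frequent by the differences shown above, about 0.6 to 1.8 points at n = 21 under the main assumptions, and in some further trials it comes one case earlier. Meeting a rule also permits the sponsor to unblind the participants involved. Four participants would be 4/21 = 19% of the trial, so any unblinding should be limited to what the safety review needs.

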**For individual participants:**

Participants who develop a severe adverse event or laboratory abnormality will not receive any additional doses and will be monitored until resolution of the AE or the return of laboratory abnormality to the acceptable screening value(s). Study drug may be re-initiated after consultation with medical monitor and sponsor. Any participant with:

- elevated ALT or AST greater than 5 X ULN should have dosing with study drug stopped and have laboratory tests repeated every 3-4 days until levels return to less than or equal to 1.5 X ULN. If the medical monitor and investigator are in agreement, study drug may be continued while a confirmatory ALT/AST is obtained within 3 days. If the confirmatory ALT/AST tests are below 5 X ULN, study drug may be continued. The frequency of the laboratory tests may be modified after discussion with the medical monitor if the liver enzymes are in a decreasing trend.
- elevated ALT or AST greater than 3 X ULN in combination with total bilirubin > 2 X ULN or INR > 1.5 X ULN OR an ALT or AST > 3 X ULN with the appearance of fatigue, nausea, vomiting, right upper quadrant pain or tenderness, fever, rash, and/or eosinophilia (>5%) should have dosing with study drug stopped and have

laboratory testing repeated every 3-4 days. If the medical monitor and investigator are in agreement, study drug may be continued while a confirmatory laboratory testing is obtained within 3 days. If these criteria are no longer met, study drug can be continued at the discretion of the medical monitor and investigator. The frequency of the laboratory tests may be modified after discussion with the medical monitor if the laboratory tests are trending towards normal.

- An increase in serum creatinine by 0.3 mg/dL (24.4 micromol/L) or 150% of baseline that is without clinical explanation of another etiology will result in repeated serum chemistry testing within 3-7 days. If the serum creatinine elevation is confirmed on repeated testing the study drug will be discontinued. If the serum creatinine elevation resolves upon subsequent testing after study drug is discontinued the study drug may be restarted with serum creatinine monitoring at the discretion of the medical monitor and investigator.
- An increase in serum calcium to  $\geq 10.5$  mg/dl (2.63 mmol/L) that is without clinical explanation of another etiology will result in repeated serum chemistry testing within 3-7 days. If the serum calcium elevation is confirmed on repeated testing the study drug will be discontinued. If the serum calcium elevation resolves upon subsequent testing after study drug is discontinued the study drug may be restarted with serum calcium monitoring at the discretion of the medical monitor and investigator.
- Note: Fractional excretion of calcium will be monitored in each participant and interpreted in conjunction with serum creatinine and serum calcium. Given the ability of fractional excretion to fluctuate, no upper limit for discontinuing study drug based on fractional excretion of calcium has been set but it may be used as a stopping rule if persistent unexplained increases in fractional excretion of calcium are observed.

**Note:** Any unanticipated serious adverse events (SAEs) that are 'related' should be reported to the NIA within 48 hours of knowledge of the same.

